13.0 Recruitment Methods

Participants will be screened through site staff and clinicians under the direction of the site investigators. Clinicians taking part in the research project will scan intakes via telehealth (or in person when the COVID-19 pandemic allows for in person procedures) appointments for eligibility by reviewing electronic medical record information and chief complaint for presenting to appointment. At time of appointment, trained clinician/research site staff will discuss BRITEPath study option and complete eligibility screening questions.

Flyers and informed consent fact sheets used to discuss procedures and risks/benefits may be emailed or mailed for the patient to view at any time.

Participants are provided with the BRITE app during this appointment following completion of the intervention. Upon responding to follow up phone calls made by Pittsburgh/ETUDES Center research staff, the participants will be paid up to \$180 on a visa gift card type card and mailed to participants' address.

Baseline visit phone call after intervention completed at site: \$40

Week 4 Follow Up call: \$60

Week 12 Follow Up call: \$80

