Following informed consent discussion in the site's clinical setting, trained research clinical staff will implement BRITEPath intervention (described above), help participant download app, and schedule a follow up visit with the participant. Pittsburgh/ETUDES Center research staff will follow up with site clinicians or a designated primary care provider if safety issues emerge during the research phone calls following management of imminent safety/risk.

PITTSBURGH/ETUDES CENTER RESEARCH PHONE CALLS & EMR DATA

During 3 follow research phone calls the measures the research study will collect include: sociodemographic questions, the CSSRS scale & suicide scales, quality of life ratings, treatment history, barriers to treatment, readiness for treatment, attitudes toward seeking psychological help, anxiety & mania adaptive scales via the K-CAT mental health adaptive screen, substance use, depression history, treatment preferences, and if there's a family history of bipolar disorder that impacts the youth's risk for mental health problems. A waiver of HIPAA authorization to collect permission verbally over the phone will be used to access and collect medical record data. Electronic medical record information will be used to supplement treatment and service utilization and uptake of the BRITEPath intervention via the RE-AIM framework described in statistical analysis. Parents will respond to questions about their child, not themselves and youth will answer about themselves. Phone calls will take about 30-60 minutes. Once a participant is completed with the research study follow up period, they will NOT lose access to the BRITE app. They will have access to it as long as they keep it installed on their device.

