17.0 Data Management* and Confidentiality

A stepped wedge design was selected for both ethical considerations and feasibility. A stepped- wedge cluster randomized trial design involves the sequential random rollout of an intervention over multiple time periods following a “baseline” period when no cluster has been exposed. The crossover is typically in one direction, from control to intervention, and continues until all of the clusters receive the intervention with observations taken from every cluster and at each time period. All 3 studies in the ETUDES Center, and specifically, BRITEPath, will utilize this design. Prior to study start, each site will be randomly assigned to switch from.

Treatment As Usual (TAU) to the intervention. In the proposed stepped wedge design, all practices start with TAU (i.e., PCP referral to embedded MH care) and are randomized to transition to implement BRITEPath at different times. All clinics will be initially monitored for at least 2 months during TAU, followed by a staggered adoption of BRITEPath. During each time period, a new clinic will begin to use BRITEPath (order determined by block randomization). A webbased system will randomly assign the next clinic to begin.

With regard to the stated hypothesis: We will perform multilevel modeling to explore time- and intervention-level factors associated with BRITEPath’s use. We will first conduct t-tests for continuous variables and chi-square tests for categorical variables to examine baseline differences in demographic and clinical variables. We will use generalized linear mixed models (nesting for site) to examine between intervention differences in readiness. Distinguishing characteristics will be included as covariates in models examining treatment effects.

Due to the pilot nature of this study, sample size and power considerations center around the precision of confidence interval (CI) width estimation for feasibility outcomes. In this development phase (Aim 1), a sample size of 50 affords us a 95% CI width of no more than 0.28.

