We will evaluate uptake of BRITEPath by community pediatric clinics utilizing the RE-AIM framework and determine implementation outcomes as follows: Reach: Compare demographic and clinical characteristics of those patients who do versus do not (opt-out) get BRITEPath in practice for sample representativeness. Efficacy: Measure the percentage of patients for whom clinically significant reductions in depressive symptoms and suicidality as well marked improvements in functioning are obtained. Adoption: The percentage and characteristics of MH clinicians who participate in the BRITEPath study. Implementation: The percentage and characteristics of MH clinicians who follow through with BRITEPath use procedures (examining different components of app use). Maintenance: Extent BRITEPath is utilized and predictors of utilization after research support has been withdrawn.

Identifiers that will be collected via electronic data management include: name, email address, phone numbers, medical record numbers, and social security numbers for payment only. We will be collecting location data (addresses), date information (Date of Birth, admission dates, etc), and sensitive data (such as protected health information, etc).

The data will be collected on a web-based database. Data will not be stored with participant identifiers and will be coded with a participant ID #. Data may be stored on UPMC owned or University owned computers in research offices. Documents containing data will be deidentified and encrypted with a password to which only the research staff have access. The following storage devices will be used:

- Google cloud storage will be used for deidentified summary data collected from NuRelm’s webportal only. NuRelm is the app developer of BRITEPath suite of tools.

PROTOCOL TITLE: The Center for Enhancing Treatment & Utilization for Depression and Emergent Suicidality Phase 1b-Study 3-BRITEPath

- University or UPMC owned laptops and desktops
- Amazon Web services stores deidentified data of one of the measures University of Pittsburgh collects through the cat-mh.com adaptive measures. Only deidentified data will be stored here.
- UPMC MyCloud/One Drive will be used to release only identifiable data and deidentified data that is necessary for ceded/partner sites to complete data analysis per Data Use Agreements with the University of Pittsburgh
- Pitt Box will be used to share data between investigators and will only contain deidentified data.

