- University of Pittsburgh CSSD Network Operations Center Managed Server: Participant questionnaire data and interview data collected during baseline and follow up phone visits will be stored on the web database created by the Center for Clinical Trials Data Collection (CCDC) on the University of Pittsburgh managed server. NuRelm will create the portal and application tables that store intervention data and communicate to the CCDC web database will be stored on this server. Only authorized users to the tables and portals/websites developed and stored on this server have access with specific login and password information given to them by study administrators/PIs. Only particular views to the data are given to particular individuals on the study. Individuals are only given access to what they absolutely need to complete their role on the study.

Any hard copy or paper data will be stored by ID # in a locked cabinet in a locked office to which research staff only have access. No research data will be stored with identifiers on it. The key/link between the ID# and participant identifiable information will be kept separately in locked cabinets in locked research offices or in encrypted electronic documents on a Pitt or UPMC owned computer behind the firewall.

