22.0 Consent Process

INFORMED CONSENT/ *Subjects who are not yet adults (infants, children, teenagers)*

Trained research/site staff will complete verbal informed consent with participant over the phone and provide a copy of the document via email or mail. Upon obtaining informed consent, the site staff will initiate the BRITEPath intervention. Following the intervention, Pittsburgh/ETUDES Center research staff will follow up and complete research phone calls for which participants will be paid.

PROTOCOL TITLE: The Center for Enhancing Treatment & Utilization for Depression and Emergent Suicidality Phase 1b-Study 3-BRITEPath

During the informed consent discussion, the site staff will speak with the parent to obtain permission to enroll the teen in this study and consent for her or his own participation. The staff will also speak with the adolescent to obtain her or his assent. The assessor will ask the family to take the phone call in a private location to decrease confidentiality breaches and discomfort about talking about sensitive topics.

During the consent process, research/site staff will make it clear that participation is voluntary to both the parent and child participants or adult participant if they are 18 at the time of enrollment. If a minor turns 18 years old during the course of the study an additional consent process will occur via the phone to ensure ongoing willingness to participate that Pittsburgh/ETUDES trained research staff will conduct. During each baseline and follow up phone call, Pittsburgh/ETUDES trained research staff will ascertain if the parent and child are still interested in participating in the study questions prior to collecting or updating data. Both the site staff and Pittsburgh/ETUDES trained research staff will make the family aware that they do not have to immediately make the decision to consent and can take the time to think and discuss participation after they receive all the necessary consent and risk information. The staff may also say that their participation will not influence their care or relationship with care providers. The staff will encourage the family to discuss their participation and provide several minutes for adequate reflection time.

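### The baseline research call follows BRITEPath delivery, so the undated covariate rule in section 17.0 can adjust away a small part of any early effect; for depression, pre-specify a dated PHQ as a covariate

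*Combined protocol and SAP*

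**What the plan says.** All quotations are from the combined protocol and SAP.

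**Order of events.** Section 6.0 says that after consent "trained research clinical staff will implement BRITEPath intervention (described above), help participant download app, and schedule a follow up visit with the participant". Section 22.0 agrees: "Following the intervention, Pittsburgh/ETUDES Center research staff will follow up and complete research phone calls for which participants will be paid". The payment list in section 13.0 labels the first paid contact "Baseline visit phone call after intervention completed at site". That section offers up to $180 for answering follow-up calls, which is the sum of the three listed payments (40 + 60 + 80), so the baseline call is one of the three.

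**What the calls measure.** Section 6.0 begins its list with "During 3 follow research phone calls the measures the research study will collect include". The list includes the C-SSRS and other suicide scales, quality of life, anxiety and readiness for treatment, as well as demographics and history. Section 17.0 uses the word baseline for this contact: "Participant questionnaire data and interview data collected during baseline and follow up phone visits".

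**How baseline values are used.** Section 17.0 says "We will first conduct t-tests for continuous variables and chi-square tests for categorical variables to examine baseline differences in demographic and clinical variables", and then "Distinguishing characteristics will be included as covariates in models examining treatment effects". It gives no variable list, data source, date limit or significance threshold. Its RE-AIM paragraph defines efficacy as: "Measure the percentage of patients for whom clinically significant reductions in depressive symptoms and suicidality as well marked improvements in functioning are obtained". It does not name the value from which a reduction is counted.

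**The concern.** A covariate in a treatment-effect model should not itself be affected by treatment. During BRITEPath periods, the call measures are taken after the app and safety plan have been delivered. If a symptom or functioning score has already moved by then, the baseline test can flag the difference. The rule then adjusts for something that is partly the effect of interest. Counting reductions from the call would lose the same early change.

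Section 6.0 says the pilot's effect sizes would be used to design a larger trial, so a systematic shortfall could carry forward. Demographics and fixed history first recorded on the call cannot be changed by BRITEPath and are not at issue.

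**Working it through.** **The plan's own figure.** The width of a 95% interval for a proportion at N = 50, worst case p = 0.5, is 2 × 1.96 × √(0.25/50) = 0.277. This agrees with the stated maximum of 0.28. It concerns feasibility proportions and does not depend on the covariate rule.

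**Inputs.** The order of events and the covariate rule come from the documents. The documents do not give the effect size, the delay from delivery to the call, the look-back periods of the scales or the correlations (section 6.0 offers the full measures on request). I assume:
- a true effect D = −0.50 SD with unit variances;
- 25 participants per condition and no clustering;
- a share f = 0.25 or 0.50 of the effect present at the call;
- a common correlation ρ = 0.5 or 0.7 among the earlier PHQ, the call measure and the outcome;
- a flag at p < 0.05.

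**If the call measure is always adjusted for.** The adjusted effect is D − ρ·f·D = D(1 − ρf). For ρ = 0.5 and f = 0.25 this is −0.50 × 0.875 = −0.438. For ρ = 0.7 and f = 0.50 it is −0.50 × 0.65 = −0.325.

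**Under the section 17.0 rule.** The call measure enters only when flagged, so the average loss is smaller. Simulation results (200,000 trials per setting; mean estimate / root-mean-square error, RMSE):

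| ρ, f | Flagged | Section 17.0 rule on call measure | Call always in | No covariate | Earlier PHQ always in |
|---|---|---|---|---|---|
| 0.5, 0.25 | 7.2% | −0.482 / 0.274 | −0.438 / 0.256 | −0.500 / 0.283 | −0.500 / 0.248 |
| 0.5, 0.50 | 13.8% | −0.454 / 0.274 | −0.375 / 0.279 | −0.500 / 0.282 | −0.500 / 0.247 |
| 0.7, 0.25 | 7.1% | −0.475 / 0.263 | −0.412 / 0.223 | −0.500 / 0.283 | −0.500 / 0.204 |
| 0.7, 0.50 | 13.9% | −0.434 / 0.264 | −0.325 / 0.270 | −0.500 / 0.283 | −0.500 / 0.204 |

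The average loss under the rule runs from 0.500 − 0.482 = 0.018 to 0.500 − 0.434 = 0.066 SD, or 4–13%. At f = 0 there is no loss. The interval half-width for the effect is t(0.975, 48 df) × √(2/25) = 0.57 SD.

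**Separating date from selection.** Applying the same p < 0.05 rule to the earlier PHQ removes the bias but leaves RMSE at about 0.26–0.27, as with the call measure. The fall to 0.20–0.25 comes from always adjusting. With 30% of PHQ values missing at random (mean fill plus an indicator), RMSE is 0.234–0.263. PHQ adjustment beats the section 17.0 rule only if its correlation with the outcome exceeds about 0.3–0.4 when complete, or 0.4–0.5 with 30% missing.

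**Case mix.** Suppose pre-treatment severity differs by 0.3 SD between conditions. An estimate with no severity covariate is then off by 0.15–0.21 SD. The estimate that always includes the call measure is −0.26 to −0.36 if BRITEPath patients are sicker, and −0.39 to −0.51 if they are milder. The section 17.0 rule has RMSE of about 0.26–0.34, against 0.32–0.35 with no covariate.

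**The case against.** **The source is inferred.** Section 17.0 does not say that its clinical variables come from the call. They could come from the medical-record data listed in section 6.0. This stands: the call as source is an inference from sections 6.0, 13.0 and 17.0. What is certain is that the plan names neither source nor date.

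**Adjustment has a purpose.** Section 6.0 concedes that assignment cannot be concealed, and section 26.2 has clinicians invite patients from their own caseloads, so TAU and BRITEPath patients may differ in severity. A reader might infer that every main model should be limited to covariates measured before treatment. The documents do not support that. They name no pre-treatment score for suicidality or functioning, so the restricted model there has no severity covariate. Its RMSE is 0.28, against 0.26–0.27 under the section 17.0 rule, and it does no better under a 0.3 SD case-mix shift. That exchanges one possible bias for another.

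**The PHQ is an imperfect substitute.** This also stands. It serves depression only. Section 6.0 gives no date for the record PHQ-9, section 10.0 admits patients without a PHQ, and section 14.0 lets participants decline record access. Missingness may follow the referral route and so not be at random. The unbiased PHQ results above assume a PHQ that is complete or missing at random, and no case-mix difference.

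**Conclusion.** The point holds in a limited form, and it is minor. The order of events is explicit and uncontradicted. The rule as written allows covariates measured after delivery, and if it takes them from the call it can remove part of an early effect. Under the assumed inputs the average loss is 0.02–0.07 SD, well inside sampling error. The actual size cannot be known from the documents, and it is zero if nothing has changed by the call.

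A reader might go further and conclude that the comparison is invalid, or that the call must move. Neither follows. Section 6.0 explains why research activities are kept out of the clinic visit, and the problem can be handled in the analysis. Nor does dating the covariate earlier improve precision by itself; that gain comes from dropping selection by baseline test. Call timing, N = 50, the 0.28 width and the 75% criterion stand.

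**What to change.** In section 17.0:
- **Depression.** Pre-specify the last PHQ dated on or before the index appointment as a covariate that is always included and not selected by a baseline test. Use the index appointment as the cut-off in both conditions, because TAU participants have no onboarding date. State the rule for missing values.
- **Suicidality and functioning.** Report estimates with and without the call measures side by side. State that the first may remove early effect and the second is open to case-mix differences. Do not claim that either is better.
- **RE-AIM efficacy.** Do not treat the post-delivery call as a pre-treatment value when counting reductions.

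**Cost.** Analysis-plan wording, the date of the index appointment and of each PHQ, and a second model for the outcomes without an earlier score. The PHQ is already part of screening (section 10.0) and of the record extract (section 6.0). The downside is missing PHQ values, perhaps not at random. These leave some case-mix bias and reduce the precision gain, which also needs a PHQ–outcome correlation above about 0.3–0.5.

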14.0 Withdrawal of Subjects*

Youth and young adult participants and parents may be formally withdrawn by the PI's if they develop a condition that meets criteria for exclusion or if they show evidence of clinical deterioration that may require further hospitalization during the course of study participation. Participants who are at risk for suicide attempts may need to be psychiatrically hospitalized, and this may occur at any time during the course of the study. Participants will be referred to their primary care physician and further for hospitalization if their condition is unstable as manifested by suicidal ideation with the inability to voice that they can keep themselves safe, psychosis, current intoxication, mania, rapid cycling, or mixed state. With permission, the study team may consult an

PROTOCOL TITLE: The Center for Enhancing Treatment & Utilization for Depression and Emergent Suicidality Phase 1b-Study 3-BRITEPath

outpatient clinician and/or the primary care physician responsible for the treatment of the youth if it is the clinical opinion of the study team that an emergency evaluation or referral for hospitalization is indicated. Participants will be encouraged to contact their PCP or outpatient provider with any concerns reported to the study team during phone assessments. In cases of severe adverse effects, patients may be instructed to go to the nearest emergency department. Adverse events will be reported to the IRB in accordance with current procedures.

Research participants may also choose to voluntarily withdraw and should provide written notice to the PI of their decision. Data collected up until the point of receiving this notice will still be included in the research study. Participants may choose not to authorize HIPAA verbally for the researchers to collect medical record information and still participate in the remainder of study activities.

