We will develop an app-based intervention, BRITEPath that enhances the capacity of pediatric primary care to effectively manage depressed and suicidal adolescents by referral to embedded MH services. BRITEPath includes three components delivered by MH clinicians, including (1.) an electronic on-boarding procedure tool that supports MH clinicians, Guide2Brite; (2.) the adolescents' safety planning app, BRITE; and (3.) the clinician dashboard, BRITEBoard, to facilitate treatment planning and communication with other primary care providers.

2.2 The aims and hypotheses related to this specific protocol and submission are below for Phase 1b. Aims of the previous phase are in a University of Pittsburgh OSIRIS IRB protocol submission (#PRO18050281) entitled ETUDES Phase 1a-qualitative. Aims of later phases described briefly will be submitted in subsequent protocols.

PROTOCOL TITLE: The Center for Enhancing Treatment & Utilization for Depression and Emergent Suicidality Phase 1b-Study 3-BRITEPath

We will test the feasibility of using BRITEPath in community & pediatric practices using a stepped wedge design. We hypothesize that participants, parents, and clinicians will find the intervention usable and feasible to deploy. We will assess the impact of BRITEPath alone (compared to its impact as part of iCHART in later phases of the ETUDES Center, by obtaining follow-up phone assessments on suicidality, depression, and functional status at 4 and 12 weeks after intake.

Aim 1b (Phase 1b, Feasibility). We will pilot BRITEPath in sites using a stepped wedge design (50 adolescents aged 12-26 yo). Hypothesis 1b: The use of BRITEPath will decrease depressive symptoms, distress, and suicidality (any self-injurious ideation, urges, or behavior) as well as improve overall functioning compared to TAU.

Criterion for success: 75% of adolescents who receive BRITEPath will use it, and 75% of MH clinicians will use Guide2BRITE and BRITEBoard.

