4.0 Study Endpoints*

At anytime, the primary investigators may discontinue a participant's participation in this study. The PI may decide to remove a participant off this study if their health or safety may be at risk; if they have not been following study instructions or because of a study administrative decision by the PI.

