We recognize the limitations of the proposed stepped wedge study design for evaluating the effectiveness of BRITEPath, once a practice enters their intervention phase, assignment to BRITEPath cannot be concealed. This concern is somewhat mitigated by blind follow-up assessors. Alternative study designs (e.g., randomized control trial) pose significant implementation challenges. Clinicians may be hesitant to deliver TAU once the BRITEPath intervention is known, which could lead to study condition contamination (e.g., BRITEPath strategies introduced into TAU condition) and nonrandom patient assignment to condition (e.g., more high acuity patients referred to BRITEPath). In a stepped wedge design these feasibility concerns are addressed by the eventual assignment of all participating practices to the intervention condition and BRITEPath can be offered to all patients moving forward. Additionally, these designs are consistent with our broader goal of enhancing participant and community stakeholder engagement with the ETUDES Center. Results from this pilot trial will allow us to estimate the effect size of the BRITEPath intervention compared to TAU for reducing suicide risk in pediatric primary care. If our initial results show promise, these effect size estimates would be used to design a larger and adequately powered randomized control trial of BRITEPath.

SCREENING

Trained research staff or site staff will determine appropriate potential participants to refer and either refer via email, phone, or in person when staff person is on site. Site staff will review medical record or be made aware of the potential participant's chief complaint at presentation to the clinical setting to determine eligibility. At the time of identifying an eligible participant, trained research staff will complete verbal eligibility screen (with parent if a minor participant is involved or with adult participant). Upon eligibility, trained research site staff will enter participant contact information and date of birth into University of Pittsburgh secure webapp saved behind a firewall. This will create an "ID" which

PROTOCOL TITLE: The Center for Enhancing Treatment & Utilization for Depression and Emergent Suicidality Phase 1b-Study 3-BRITEPath

will communicate with the electronic Guide2Brite to create a profile for the participant in the secure BRITEPath web app.

STUDY INTERVENTION

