10.0 Inclusion and Exclusion Criteria*

Individuals will be screened for eligibility via phone or after presenting to the site's clinical setting with an eligibility script and inclusion/exclusion questions. Responses to the questions will be entered into a secure study database managed by the University of Pittsburgh housed on a secure, encrypted server behind University firewall. Individual logins will be provided to research/site staff associated with this project.

Inclusion Criteria:

- Youth aged 12-26 yo
- Own a device (e.g. smartphone, ipod, tablet) with capability to download BRITE app
- Biological or adoptive parent is willing to provide informed consent for teen to participate
- Youth speaks and understands English
- Positive PHQ score or provider determines patient has depressive symptoms based on clinical interaction and refers youth to the study (in cases when PHQ is not available OR provider/parent have concern that youth/patient has a mood or behavioral problem
- Family agrees to see a MH staff at the site

Exclusion Criteria:

- Non English speaking
- No parent willing to provide informed consent for minors
- No cell phone capability of downloading BRITE app
- Is currently experiencing mania or psychosis symptoms that would prevent participant from understanding/participating
- Evidence of an intellectual or developmental disorder (IDD)
- Life threatening medical condition that requires immediate treatment (included emergent suicidality, homicidality, abuse/neglect, or other mental or physical condition)
- Other cognitive or medical condition preventing youth from understanding study and/or participating.
- Adults unable to consent
- Pregnant women-not specifically included or excluded as intervention and research procedures conducted will not inquire if a woman is pregnant.

-Prisoners excluded

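### PIs can remove participants from the study on grounds that overlap the outcomes, with no stated provision to continue the week 4 and week 12 calls

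*Combined protocol and SAP*

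**What the plan says.** **Grounds for removal.** Section 14.0 allows the PIs to withdraw participants who come to meet an exclusion criterion, or "if they show evidence of clinical deterioration that may require further hospitalization during the course of study participation". One of the exclusion criteria in Section 10.0 is "Life threatening medical condition that requires immediate treatment (included emergent suicidality, homicidality, abuse/neglect, or other mental or physical condition". Section 4.0 adds: "The PI may decide to remove a participant off this study if their health or safety may be at risk". It also allows removal for not following study instructions or for administrative reasons. All of this is discretionary.

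**Outcomes.** Hypothesis 1b in Section 2.0 is that "The use of BRITEPath will decrease depressive symptoms, distress, and suicidality", and improve functioning, compared with TAU. The same section plans "obtaining follow-up phone assessments on suicidality, depression, and functional status at 4 and 12 weeks after intake".

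**Data after withdrawal.** The one rule on data, in Section 14.0, follows the sentence on voluntary withdrawal by written notice: "Data collected up until the point of receiving this notice will still be included in the research study". It keeps what was already collected and does not mention later calls.

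**Analysis.** Section 17.0 names t-tests, chi-square tests, multilevel and generalized linear mixed models, and a RE-AIM Efficacy percentage. It gives no analysis set, no rule for missing outcomes and no denominator for that percentage.

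**Use of the results.** Section 6.0 says that, if the pilot is promising, "these effect size estimates would be used to design a larger and adequately powered randomized control trial of BRITEPath".

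**The concern.** A participant who deteriorates is one whose week 4 and week 12 scores matter most to the comparison. If the PIs remove that person from the study and the calls stop, the outcome is missing because of the outcome. Mixed models can use partial data, but deterioration seen between calls may never enter the observed data, so the loss may not be missing at random.

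The loss could also differ by condition. Section 6.0 accepts that assignment cannot be concealed once a practice crosses over. The follow-up assessors are blind, but nothing says that the PIs' withdrawal decision is. At stake are the effect sizes that would feed the design of a larger trial.

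**Working it through.** **Step 1. Is removal from the study or only from the intervention?** Section 14.0 alone says only that participants may be formally withdrawn. Section 4.0 is explicit that participation in the study can be ended, and the SAE definition in Section 18.0 refers to termination from the study. TAU participants have no app to stop, so for them withdrawal can only mean leaving the study.

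**Step 2. Do the grounds overlap the outcomes?** Set side by side:
- Deterioration that may lead to hospitalization (Section 14.0) against depressive symptoms, distress and functioning (Section 2.0).
- Emergent suicidality, within a life-threatening condition needing immediate treatment (Section 10.0), against suicidality (Section 2.0).

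The overlap is real, but it lies at the severe end.

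**Step 3. What is still collected after a PI removal?** The only follow-up stated to run past termination is the 30-day SAE window in Section 18.0. For a participant removed at the end of week 2, it closes on day 14 + 30 = 44. Week 12 is day 84, so 84 − 44 = 40 days are uncovered. Records (Section 6.0) can supply service use and clinic PHQ-9 scores, but not the scheduled suicidality and functioning interviews. Section 14.0 also lets participants decline record access.

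**Step 4. The plan's own precision figure.** Section 17.0 states a 95% CI width of no more than 0.28 at n = 50. The Wald width at p = 0.5 is 2 × 1.96 × √(0.25/50) = 0.277, which reproduces it. That figure is for feasibility outcomes and serves here only as a yardstick.

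**Step 5. Illustration of the denominator.** The documents give no withdrawal rate, split by condition or improvement rate. Assume 25 of the 50 participants are in BRITEPath, 12 improve, and everyone withdrawn is unimproved.

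| Withdrawn | All enrolled, withdrawn counted as not improved | Withdrawn left out | Shift |
|---|---|---|---|
| 1 | 12/25 = 48.0% | 12/24 = 50.0% | +2.0 points |
| 2 | 12/25 = 48.0% | 12/23 = 52.2% | +4.2 points |
| 3 | 12/25 = 48.0% | 12/22 = 54.5% | +6.5 points |

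The half-width of a 95% CI at n = 25 is 1.96 × √(0.48 × 0.52/25) = 0.196, about 20 points, before any allowance for site clustering.

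**Step 6. Illustration of the comparison.** Assume 25 per condition and 10 improved in each, so no true difference. Leaving out 5 unimproved BRITEPath participants and no TAU participants gives 10/20 = 50% against 10/25 = 40%, a spurious +10 points. Reversing the counts gives −10 points. The sign depends on where the withdrawals fall. Clustering and time period are ignored.

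**The case against.** The best case against the point is that the documents expect deterioration within follow-up and keep withdrawal for the extreme end. Section 15.0 says youth with current suicidal ideation may be eligible. It also sets out how interviewers manage ideation or behavior disclosed on calls, without mentioning withdrawal. Section 14.0 says hospitalization may happen at any time during the study. Section 18.0 plans an ongoing CONSORT diagram and early-termination reports. All of this stands and limits the likely number of losses. None of it says that the calls continue after a PI removal, and counting losses does not recover the week 4 and week 12 measures.

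A second objection is that a missing analysis set affects all attrition, including ordinary non-response. That is right, and alone it would only be missing detail. It supports the point here but is not its core.

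A reader might go further and infer any of three things that the documents do not support:
- **That the BRITEPath effect is overstated.** With no withdrawal rate, neither size nor direction can be claimed.
- **That the Efficacy percentage is inflated.** Section 17.0's wording can be read as covering all patients. If those withdrawn stay in the denominator and count as not improved, nothing is inflated.
- **That participants who deteriorate are left without care.** Section 14.0 refers unstable participants to primary care and on to hospitalization, and Sections 6.0 and 15.0 keep standard-care risk management in place. What may end is the repeated research assessment that Section 15.0 describes as an extra safeguard.

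**Conclusion.** The point holds in a limited form. As written, the PIs may remove participants from the study for reasons that overlap the outcomes, and no text available for review continues outcome follow-up afterwards. This is an avoidable source of outcome-related missing data, not a demonstrated large bias. The illustrated shifts of 2.0 to 6.5 points rest on assumed counts and are smaller than the roughly 20-point half-width at n = 25.

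It deserves action because the remedy is cheap and the pilot's effect sizes may be carried forward. Confidence is moderate: the consent script and the Fact Sheet (mentioned in Sections 15.0 and 23.0) were not in the text reviewed and may settle the matter.

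**What to change.** Leave the clinical decision rules as they are.

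- **Sections 4.0 and 14.0:** state that a PI decision to discontinue a participant, in either the TAU or the BRITEPath condition, does not by itself end outcome follow-up. The planned week 4 and week 12 calls and authorised record capture continue unless the participant or parent withdraws consent or the participant cannot be interviewed. Wording limited to stopping BRITEPath would not reach TAU participants and could itself create unequal loss.
- **Consent script and Fact Sheet:** check that they agree.
- **Section 17.0, as support:** analyse all enrolled participants by their site's condition at enrolment. Report the Efficacy percentage per condition, with that condition's enrolled participants as denominator. State how participants without week 12 data are counted, for example as not improved, with an observed-case sensitivity analysis. Report PI withdrawals by condition, with reason and timing, building on the CONSORT diagram and early-termination reports.

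**Cost.** A few sentences, IRB review of the wording, and some retention effort. Section 13.0 ties payment to answered calls ("Upon responding to follow up phone calls made by Pittsburgh/ETUDES Center research staff"). Compared with ending the calls, each participant removed before week 4 would therefore add up to $60 + $80 = $140 and two interviews of 30 to 60 minutes. Those payments are already planned for every participant.
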